9.4.3 ANALYSIS OF THE SECONDARY ENDPOINT(S)

Statistical Analyses: As in the primary aim analyses, we will employ linear mixed models featuring fixed effects and random effects to account for within subject variation. We will also perform a differences-indifferences analysis comparing change between baseline and the end of the intervention to determine which strategy resulted in greater improvement in PF.

Statistical Analyses: As in the primary aim analyses, we will employ linear mixed models featuring fixed effects and random effects to account for within subject variation. We will also perform a differences-indifferences analysis comparing change between baseline and the end of the intervention to determine which strategy resulted in greater improvement in PF. Statistical Analyses: In addition to unadjusted comparisons, we will employ multiple linear regression models.

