3 OBJECTIVES AND ENDPOINTS

OBJECTIVES	ENDPOINTS	JUSTIFICATION FOR ENDPOINTS
Primary		
The primary objective of this study is to develop and validate a multi- modal digital pain reduction kit for improving physical function over time.	The primary endpoint in this study is a clinically significant change in self- reported physical function over time among individuals in the intervention arm compared to those in the active control. The outcome measure used to quantify this endpoint is the PROMIS® PF short-form, a validated self-report of physical function. The	The PROMIS® PF short- form scale is a widely validated instrument with excellent content validity, construct validity, and reliability in patients with spinal disorders and other conditions marked by

OBJECTIVES	ENDPOINTS	JUSTIFICATION FOR ENDPOINTS
	outcome measure is administered on a weekly basis via a smartphone survey to capture longitudinal change and variation among participants.	diminished mobility. The outcome measure allows us to place patients on a continuum of physical function with respect to various physical actions.
Secondary		
The secondary objective of this study is to investigate the efficacy of a multi-modal digital pain reduction kit in reducing pain interference over time, work productivity, opioid use, and satisfaction with care.	The secondary endpoints of are clinically significant changes in pain interference, work productivity, use of opioids, and satisfaction with healthcare among those in the intervention arm compared to participants in the active control. Outcome measures include pain interference (PROMIS® Pain Interference, measured weekly via smartphone surveys), work absenteeism and presenteeism (WPAI:LB, measured at baseline and exit surveys), number of 90 Morphine Milligram Equivalent opioid prescriptions (obtained via cumulative EHR records), and satisfaction with healthcare (CG- CAHPS, measured once at the conclusion of the study).	
Tertiary/Exploratory		
N/A	N/A	N/A

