4 STUDY DESIGN

4.1 OVERALL DESIGN

This RCT will enroll 174 patients with pain due to musculoskeletal injuries to test the efficacy of a multi- model digital pain reduction kit on short term pain management as an adjunct to traditional medical therapy. We will attempt to enroll a minimum of 90 patients reporting lower back pain specifically, as patients without lower back pain are less likely to use the TENS unit. Prior to adding the TENS unit to the control arm, we recruited 24 control patients. However, we will not discard their data since we intend on performing a supplementary sensitivity analysis. In addition to these 24 controls, we will randomize 75 patients to receive the study intervention (multi-modal digital pain-reduction kit with optional remote coaching support), and the other 75 patients will receive an active control. We will allocate patients using a random number generator to ensure that there is an equal distribution of participants in the control vs. experimental group. The primary outcome will be changes in self-reported physical function measured by the Patient Reported Outcome Measurement Information System (PROMIS®) Physical Function Scale. Secondary outcomes will include PROMIS® Pain Interference Scale, PROMIS® Global Health Scale, work productivity and activity impairment questionnaire (WPAI) (for patients with lower back pain specifically), patient satisfaction measured by the Pain Treatment Satisfaction Scale and SF Patient-Satisfaction Questionnaire), and use of opioids (measure in morphine milligram equivalents).

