5.5 STRATEGIES FOR RECRUITMENT AND RETENTION

Male and female participants above the age of 18 will be screened to reach target enrollment 174 patients over a period of 16 months. Participants presenting with pain due to a musculoskeletal injury will be screened and enrolled at four sites (Cedars Sinai Orthopedic Clinic, Medical Delivery Network, Cedars Sinai Pain Management Clinic, Medical College of Wisconsin). Patients will be identified and approached by their providers. The treating physicians will contact their patients during their clinic visits and assess the patient's willingness to be contacted about the research and the treating physician will document the patient's willingness to be contacted on the *CSMS Research Interest* letter. The Research Letter will be tailored to each clinical practice of the treating provider. Additionally, participating providers will distribute recruitment pamphlets to patients in clinic and/or through mail. Should the patient be interested in being contacted about the study, the study team will then approach the patient for

participation in the research either in person or over-the-phone. The patient will have the option to complete their consent forms on paper or electronically using the 21 CFR 11-compliant online platform, DocuSign. Every subject will be informed of the approximate time to complete the consent process. Consenting will be done with a research staff member either in-person or remotely via DocuSign to ensure the identity of the person signing the informed consent form is indeed the subject participating in the research study. A copy of the informed consent documents will be given to the participants for their records via their email or a physical hard copy. Participants who consent remotely will receive their study equipment through a secure FedEx package requiring a signature. Retention to the 60-day study for the intervention group will be managed using weekly reminders to complete survey protocols, as well as optional opt-in monitoring of compliance and health data via remote clinical and technical support staff. Participants will not receive monetary compensation for participating in this study.

Participants experiencing lower back pain will be oversampled to a minimum of 45 per arm in order to obtain sufficient sample size for testing the success of the TENS unit.

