9 STATISTICAL CONSIDERATIONS

9.1 STATISTICAL HYPOTHESES

• Primary Efficacy Endpoint(s):

Primary Outcome: Physical function over time as measured by PROMIS PF score (T- Scored, Continuous)

Question: Which intervention is more effective in improving physical function?

Independent variable of interest: Comparator received, intervention vs. control (Dichotomous)

Potential Covariates: Age, gender, race, ethnicity, mental health comorbidities, chronic pain diagnosis, use of other pain medications (neuropathic pain medications, NSAIDS, antidepressants), benzodiazepine use, number of office visits during study period, baseline PROMIS[®] scores, encounter month, physician years of practice, physician gender.

• Secondary Efficacy Endpoint(s):

Secondary Outcome: Pain over time as measured by PROMIS Pain Interference Score (T-Scored, Continuous)

Question: Which intervention is more effective in improving patient's pain interference?

Independent variable of interest: Comparator received, intervention vs. control (Dichotomous).

Potential Covariates: Same as Primary Aim.

Secondary Outcome: Effects of lower back pain symptom severity on work productivity and regular activities over time as measured by WPAI:LB (T-Scored, Continuous).

Question: Which intervention is more effective in improving patient's work productivity and participation in regular activities?

Independent variable of interest: Comparator received, intervention vs. control (Dichotomous).

Potential Covariates: Same as Primary Aim.

Secondary Outcome: New Opioid Prescription over 90MME (Dichotomous)

Question: Which intervention is more effective in reducing opioid prescriptions of 90 Morphine Milligram Equivalents (MME) or greater?

Independent variable of interest: Comparator received, intervention vs. control (Dichotomous).

Potential Covariates: Same as Primary Aim.

Statistical Analyses: As in the primary aim analyses, we will employ mixed effects models featuring both fixed effects and random effects to account for within subject variation.

Because this particular outcome is binary, we will use mixed logistic regressions in which the log odds of the outcomes are modeled as a linear combination of the predictors.

Secondary Outcome: Satisfaction with Pain Treatment and Healthcare Scores

Question: Which intervention is more effective in improving how satisfied patients feel with their care?

Dependent variable: Pain Treatment and Patient Satisfaction Scores

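### Work productivity (WPAI) has only a Day 1 and a Day 60 value, but the plan does not say how the Day 1 value enters the mixed model, adds a less precise change-score analysis, and omits baseline WPAI from the covariates

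*Combined protocol and SAP*

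**What the plan says.** Section 3 lists "work absenteeism and presenteeism (WPAI:LB, measured at baseline and exit surveys"; the schedule in 1.3 marks the same two occasions, Day 1 and Day 60. Section 4.1 limits the instrument to patients with lower back pain, who under 5.5 are to be "oversampled to a minimum of 45 per arm".

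Section 9.1 introduces the outcome as "Secondary Outcome: Effects of lower back pain symptom severity on work productivity and regular activities over time as measured by WPAI:LB". Its covariate entry reads "Potential Covariates: Same as Primary Aim". The primary-aim list contains "number of office visits during study period, baseline PROMIS[®] scores, encounter month" among other items, but no baseline WPAI.

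Section 9.4.3 has two identical paragraphs followed by a sentence on multiple linear regression. None of them names its outcome. By the order of outcomes in 9.1, where the opioid outcome has its own logistic model, the second paragraph is the one for WPAI. It says first that "we will employ linear mixed models featuring fixed effects and random effects to account for within subject variation", and then: "We will also perform a differences-indifferences analysis comparing change between baseline and the end of the intervention". The sentence ends by naming PF as the quantity compared. The paragraph does not state the treatment term, whether Day 1 is part of the outcome vector, or whether the arms share a baseline mean.

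**The concern.** With one value before treatment and one after, the use made of the first largely determines the precision of the comparison. A difference-in-differences subtracts the Day 1 value in full. Regression on the Day 1 value removes only as much as the correlation justifies, so it has smaller variance at any correlation below 1. Below r = 0.5 the change score is noisier than ignoring Day 1 altogether.

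The plan accepts baseline adjustment for PROMIS outcomes. Carrying that list over to WPAI leaves out the baseline that matters for this outcome. WPAI is confined to the back-pain patients, so precision is already limited. The mixed model could avoid the loss, but only in a form that the plan does not state.

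**Working it through.** **Inputs.** Two WPAI values per patient (1.3, 3). A minimum of 45 back-pain patients per arm (5.5). Withdrawal 25%, power 80% and level 0.05 (9.2, written for PF; two-sided assumed). The documents give no sample size, effect size or power figure for WPAI, so there is none to reproduce. The correlation r is not in the documents; 0.3 to 0.7 is assumed. Equal SDs at both visits are assumed, with Day 60 SD = 1.

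**Completers.** 45 × 0.75 = 33.75; 33 per arm is used below.

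**Variance per patient.**
- Change score: 2(1−r)
- Adjusted for Day 1: 1−r²
- Day 60 alone: 1
- Ratio, adjusted to change: (1−r²)/[2(1−r)] = (1+r)/2

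The ratio is 0.65, 0.75 and 0.85 at r = 0.3, 0.5 and 0.7. Its inverse, 2/(1+r), is 1.54, 1.33 and 1.18, so the change score needs 54%, 33% or 18% more patients for equal precision.

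**Detectable difference** (80% power) = (1.960 + 0.842) × √(2V/n), where V is the variance above. For V = 1 this is 0.690 SD at n = 33 and 0.591 SD at n = 45.

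| r | n=33, change | n=33, adjusted | n=45, change | n=45, adjusted |
|---|---|---|---|---|
| 0.3 | 0.82 | 0.66 | 0.70 | 0.56 |
| 0.5 | 0.69 | 0.60 | 0.59 | 0.51 |
| 0.7 | 0.53 | 0.49 | 0.46 | 0.42 |

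**What the mixed model would do.** Three forms fit the wording of 9.4.3. They were compared by simulation with 33 per arm, 2,000 trials per value of r, and a true Day 60 effect of 0.60 SD.

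1. *Arm, time and arm-by-time, random intercept.* With complete data at two time points, the interaction is the difference in mean change. It matched the difference-in-differences in the simulation.
2. *Arm main effect only.* The one model written out, in 9.4.4, has time, arm and TENS, with no arm-by-time term. If Day 1 is in the outcome vector, the arm coefficient averages a Day 1 difference of zero with the Day 60 effect: (0 + 0.60)/2 = 0.30. The simulated means were 0.307, 0.305 and 0.300.
3. *Baseline means constrained equal across arms.* This performs like regression on Day 1.

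Standard deviation of the estimated effect:

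| r | Change score or form 1 | Regression on Day 1 | Form 3 |
|---|---|---|---|
| 0.3 | 0.292 | 0.233 | 0.231 |
| 0.5 | 0.240 | 0.217 | 0.214 |
| 0.7 | 0.189 | 0.176 | 0.174 |

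The formula √(2V/33) gives 0.291, 0.246 and 0.191 for the change score, and 0.235, 0.213 and 0.176 for the adjusted analysis.

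**Effect of adding the covariate alone.** In form 1, a covariate that is constant within a patient cancels from the within-patient difference. With complete data, adding Day 1 WPAI to that model therefore leaves the arm-by-time estimate unchanged. The model form has to change as well as the list.

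**The case against.** A reader might infer that WPAI is analysed only as a change score. The documents do not support that: 9.4.3 puts a linear mixed model first and adds the difference-in-differences to it. No section states an arm-by-time term for that model, and a constrained-baseline version would lose nothing. This stands, and it limits the point about the mixed model to one of missing specification.

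A reader might also infer that the covariate list itself causes the loss. That does not follow. The list is headed as potential covariates, so it is not closed, and adding baseline WPAI to a model that keeps Day 1 as an outcome recovers nothing.

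The size is also open to challenge. The correlation is assumed, and at r = 0.7 the gain is only 0.04 SD. Baseline PROMIS covariates may recover part of the loss; the documents do not allow this to be sized. The 45 per arm is a minimum, 7.2 provides for replacing withdrawn participants, and the intention-to-treat comparison in 9.4.4 also keeps the earlier controls without TENS, whose back-pain share is not given. The columns for 45 per arm show the effect of larger numbers; the variance ratio does not depend on them.

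None of this removes the core. The stated difference-in-differences is less precise at any r below 1, and the one mixed-model form that avoids the loss is not written anywhere.

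**Conclusion.** The point holds as a matter of specification and precision on a secondary endpoint. The planned difference-in-differences has 1.18 to 1.54 times the variance of a baseline-adjusted analysis for r between 0.7 and 0.3, assuming equal SDs. The lead mixed model either shares that loss, estimates half of the Day 60 effect, or avoids both problems, depending on terms that the plan leaves open. As printed, the difference-in-differences contrast does not refer to WPAI at all.

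A reader might take this to mean that the WPAI comparison would be biased or would miss its power. Neither is supported: the change score is unbiased under randomisation, and the plan sets no WPAI effect size or power target that could be missed. The change is a worthwhile gain at no cost, not the repair of an invalid analysis.

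**What to change.** In 9.4.3, replace both the mixed model and the difference-in-differences for WPAI with one baseline-adjusted analysis of each WPAI score, in one of two forms:

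- linear regression of the Day 60 score on arm and the patient's own Day 1 value of the same score, with Day 1 not also used as an outcome; or
- a mixed model for both visits with baseline means constrained equal across arms and the Day 60 arm difference as the treatment effect.

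The second form also keeps patients with only one WPAI value, which fits the all-randomised dataset in 9.3. The regression drops patients without a Day 1 or Day 60 value unless the missing value is imputed, so the plan should say which applies.

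In 9.1, list the baseline value of the same WPAI score as a covariate if the regression form is chosen. In 9.4.3, name the outcome that each paragraph covers and replace the reference to PF with that outcome.

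The cost is wording in 9.1 and 9.4.3. The Day 1 WPAI is already in the schedule, so no data collection changes.

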9.4.4 ACCOMODATING ADDITION OF TENS UNIT TO THE CONTROL ARM

An ITT analysis "Includes all randomized patients in the groups to which they were randomly assigned, regardless of their adherence with the entry criteria, regardless of the treatment they actually received, and regardless of subsequent withdrawal from treatment or deviation from the protocol."^{ref} Accordingly, we will follow the original analysis plan described above with regard to analyzing results by study-arm. In addition to the ITT analysis, however, we will conduct a sensitivity analysis by repeating the statistical procedures in a per-protocol fashion wherein the members of the control arm who did not receive a TENS unit will be dropped from the sample. Directions, magnitudes, and significance of treatment effects will be presented for both analyses.

Furthermore, because the TENS unit will appear in both study arms - and unevenly in the control arm – we recognize that an ITT analysis strictly *by* study-arm risks misidentifying the effect of treatment, while a per-protocol analysis risks introduction of bias. Therefore, we will conduct an additional linear mixed model regression analysis using a term for the TENS that captures the effect of the TENS separately from the effects of study-arm assignment. The model used to fit these data is as follows:

 $\hat{y}_{it} = \beta_0 + \beta_1 time_{it} + \beta_2 study_arm_{it} + \beta_3 TENS_{it} + e_{it}$

where time represents change in time from baseline, study_arm indicates status as a control or experimental participant (0= control and 1=experimental), *i* is the individual participant, and TENS indicates TENS unit usage (0= no TENS unit and 1=TENS unit). We can therefore write a regression equation describing each type of patient differentiated by the addition of the TENS unit to control conditions:

Treatment: $\hat{y}_{it} = \beta_0 + \beta_1 time_{it} + \beta_2 study_arm_{it} + \beta_3 TENS_{it} + e_{it}$

Control w/o TENS: $\hat{y}_{it} = \beta_0 + \beta_1 time_{it} + e_{it}$

Control w/ TENS:

 $\hat{y}_{it} = \beta_0 + \beta_1 time_{it} + \beta_3 TENS_{it} + e_{it}$

In this manner we isolate the term of interest (study_arm). Given we are only adding one term but 20 subjects, we are comfortable relying on the original power calculation.

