1.1 SYNOPSIS	
Title:	Development and validation of a digital pain-reduction kit for musculoskeletal injuries
Study Description:	This study will test the effectiveness of an evidence-based, multi-modal, "digital pain-reduction kit" as a non-pharmacological supplement to managing patients with pain due to musculoskeletal injuries. Outpatients will be randomized to receive either the pain reduction kit or an active control. The kit will contain a virtual reality (VR) headset, therapeutic VR visualization software, a low-cost wearable transcutaneous electrical nerve stimulation (TENS) unit. The control group will receive a TENS unit; they will not receive VR, or remote coaching. Study devices will be delivered to the patient's home with instructions for use; patients will receive remote clinical and technical support. Patients will be followed for 60 days and monitored for functional status, pain levels, use of pain medications (including opioids), satisfaction with care, and time to returning to work. Participants will also be asked to consent/authorization to access medical records from their treating facility (if a non-CSMC site).
Objectives:	Primary Objective: The primary objective of this study is to develop and validate a multi-modal digital pain reduction kit for improving physical function over time. Secondary Objective: The secondary objective of this study is to investigate the efficacy of a multi-modal digital pain reduction kit in reducing pain interference over time, work productivity, opioid use, and satisfaction with care.
Endpoints:	Primary Endpoint: The primary outcome measures in this study are weekly surveys (PROMIS® PF short-form) of self-reported physical function. Secondary Endpoints: The secondary outcome measures in this study are pain interference (PROMIS® Pain Interference), work absenteeism and presenteeism (WPAI:LB), number of 90 Morphine Milligram Equivalent opioid prescriptions, and satisfaction with healthcare (Pain Treatment Satisfaction Scale and SF Patient-Satisfaction Questionnaire).
Study Population:	The study consists of 174 English adults (75 intervention; 75 control with TENS; 24 control without TENS) in the Greater Los Angeles Area presenting with pain from musculoskeletal injuries.
Phase:	N/A
Description of	Cedars-Sinai Medical Center Orthopedic Clinic
Sites/Facilities Enrolling	Cedars-Sinai Medical Delivery Network (MDN)
Participants:	Medical College of Wisconsin (MCW)

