6.2 MEASURES TO MINIMIZE BIAS: RANDOMIZATION AND BLINDING

Per the new protocol, participants will be randomized intervention or control until intervention and control groups each have 75 enrollees. In addition to these 150 participants, the group of 24 controls that were originally recruited without the TENS unit will remain accounted for in the supplementary analysis. There will be no blinding, as participants in the control group will be aware that they are missing components of the intervention as detailed in the consent form.

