To collect the patient reported outcomes (PROs) for this study, we will use ecological momentary assessment (EMA) software (LifeData), a HIPAA-compliant, cloud-based survey administration platform capable of administering surveys in real-time. We will also allow patients use Redcap as an alternative program to collect PROs. With this program the patient doesn't have to use an app on their phone and instead just respond to surveys sent to their email address. To administer PROs, we will upload a list of patient email addresses into their HIPAA-compliant website which in turn allows scheduled administration of PRO questionnaires at daily and weekly intervals. Each week, the EMA app will send patients a reminder to fill out the scheduled PROs. If they do not fill them out, they will be sent a reminder prompt. The data collected by LifeData or Redcap will then be downloaded into a secure analysis and visualization file accessible to the research team and the Digitalist.

Work Productivity and Activity Impairment

Work productivity can be measured in terms of absenteeism (missing work) and presenteeism (diminished productivity at work). The Work Productivity and Activity Impairment (WPAI) questionnaire is a validated, widely used, brief, 6-item questionnaire that measures absenteeism and presenteeism related to specific health conditions.

Use of Opioids

In order to capture medication use related to their injury, including the use of opioids, we will link patient electronic health record (EHR) data to the other data sources using Medical Record Numbers and date of birth. We will collect opioid prescription information using pharmaceutical claims data, and also collect information on medications commonly used by individuals with chronic pain conditions. Prescribed opioid medications include: codeine, dihydrocodeine, tramadol, morphine, hydromorphone, oxymorphone, tapentadol, buprenorphine, methadone, oxycodone, fentanyl, remifentanil. We will convert all opioid doses into a single metric using morphine milligram equivalents (MME).

Satisfaction with Pain Treatment and Healthcare Surveys

We will evaluate patient experience data as measured by the 39-item Pain Treatment Satisfaction Scale and the 18-item short-form version of the Patient-Satisfaction Questionnaire. Both questionnaires are validated for use in studies to compare patient satisfaction between different treatment assignments.

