9.3 POPULATIONS FOR ANALYSES

All randomized participants will be included in the dataset (ITT).

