10.3 PROTOCOL AMENDMENT HISTORY

The table below is intended to capture changes of IRB-approved versions of the protocol, including a description of the change and rationale. A Summary of Changes table for the current amendment is located in the Protocol Title Page.

Version	Date	Description of Change	Brief Rationale			
1.0	06/08/2017	Initial Protocol	N/A			
1.1	06/19/2017	Minor changes	N/A			
1.2	06/25/2017	Changed criteria	Clarification			
1.3	07/05/2017	Major changes throughout	IRB review			
1.4	07/31/2017	Minor IRB changes	IRB review (round 2)			
1.5	02/22/2018	Minor changes to questionnaires , TENS protocol, and health coach definition	Clarification			
5.4	10/22/2018	Minor changes to eligibility criteria and other sections reflecting the change	Addition of new clinical site and open recruitment for LBP.			
6.1.1	11/12/2018	Change in device used to display the audiovisual content.	The new VR headsets will be far easier for patients to use at home.			
6.2	8/7/19	Specific letters provided to patients, addition of Redcap as a method to collect PROs	For the patients comfort a letter tailored to the treating provider will be added, Redcap was added to increase the number of ways patients could provide PROs.			
6.3	8/30/19	PICO G2 added as another VR headset that patients may receive.	An update to the Oculus software rendered the intervention software inoperable. The software vendor has started to use a different but comparable VR headset. The headset they are using is called the PICO G2. It will have the exact same software provided to the patient as what was provided via the Oculus Go.			
6.4	10/4/19	Medical College of Wisconsin (MCW) added as an external study site, and [name] added as an external study team member.	The study is now multi-site with the addition of Medical College of Wisconsin (MCW) to accelerate recruitment rates.			

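### The per-protocol analysis in 9.4.4 drops the early controls but not the kit patients randomised alongside them, so the arms are no longer concurrent; the TENS-term model rests on the same contrast

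*Combined protocol and SAP*

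**What the plan says.** Section 4.1 records that "Prior to adding the TENS unit to the control arm, we recruited 24 control patients". It describes the study as an RCT and says: "We will allocate patients using a random number generator to ensure that there is an equal distribution of participants". Section 6.2 continues under the changed design: "participants will be randomized intervention or control until intervention and control groups each have 75 enrollees". The synopsis gives the total as 174: 75 kit, 75 control with TENS and 24 control without TENS.

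Section 9.3 puts all randomised participants in the ITT dataset. Section 9.4.4 keeps that analysis and adds two more. The first repeats the procedures in a per-protocol fashion, in which "the members of the control arm who did not receive a TENS unit will be dropped from the sample". The second is a mixed model with terms for time, study arm and TENS. The section concedes in general terms that a per-protocol analysis may introduce bias, and it will report direction, magnitude and significance for both the ITT and the per-protocol analyses. Encounter month and baseline PROMIS scores appear in 9.1 only as potential covariates.

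**The concern.** Being a control without TENS amounts to having been recruited before the change. The exclusion is therefore a calendar cut made in one arm only. Kit patients randomised in that period stay in, and their concurrent comparators go.

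This matters if patients or data differ between eras. The amendment history (10.3) records a new clinical site and open low-back-pain recruitment (10/22/2018), a second survey route (8/7/19) and an external site (10/4/19). Of the survey route it says "Redcap was added to increase the number of ways patients could provide PROs", and section 8.1 now states: "We will also allow patients use Redcap as an alternative program to collect PROs". Such changes can alter case mix and who responds. Any resulting era difference would be read as a kit effect, in the analysis most likely to be taken as the clean comparison of kit with TENS alone. Because the TENS-term model shares the contrast, agreement between the two added analyses could be mistaken for robustness.

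**Working it through.** **Inputs from the documents.** 24 early controls (4.1); 75 kit, 75 control with TENS and 24 control without (1.1); equal allocation intended (4.1); effect size 0.6 SD, alpha 0.05 and 25% withdrawal (9.2); MCID 2 T-score points = 0.2 SD (8.1). The plan gives no figure for this problem. Its only relevant count reproduces: 75 + 75 + 24 = 174.

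**Assumptions.** The number of early kit patients, k, is not stated. Equal allocation suggests about 24; I show 15 to 33. Era shifts of 0.2 and 0.3 SD are illustrations. Tests are two-sided and normal on a single between-patient comparison with unit SD; repeated measures are ignored.

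**Early-era share.** With k = 24 the per-protocol set has 24/75 = 32% early kit patients against 0/75 = 0% early controls. In the ITT set the shares are 24/75 = 32% and 24/99 = 24%. Dropping the early controls widens the gap from 8 to 32 percentage points. The 174 count has no separate cell for early kit patients, so they appear to lie within the 75. If 75 new kit patients came on top of 24 early ones, the share is 24/99 = 24%.

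**Bias and false-positive rate with no kit effect.** Bias b = share × era shift. SE = sqrt(1/75 + 1/75) = 0.163 SD with no loss, and sqrt(1/56 + 1/56) = 0.189 SD with 25% loss (75 × 0.75 ≈ 56). Rate = Φ(−1.96 − b/SE) + 1 − Φ(1.96 − b/SE).

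| k | share | shift (SD) | bias (SD) | 75 v 75 | 56 v 56 |
|---|---|---|---|---|---|
| 15 | 20% | 0.2 | 0.04 | 5.7% | 5.5% |
| 24 | 32% | 0.2 | 0.06 | 6.8% | 6.3% |
| 33 | 44% | 0.2 | 0.09 | 8.4% | 7.5% |
| 15 | 20% | 0.3 | 0.06 | 6.6% | 6.2% |
| 24 | 32% | 0.3 | 0.10 | 9.0% | 8.0% |
| 33 | 44% | 0.3 | 0.13 | 12.8% | 10.7% |

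On the 99-kit reading (99 v 75, SE 0.153) the biases are 0.05 and 0.07 SD and the rates 6.2% and 7.6%.

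**TENS-term model.** At a given time the three groups have means β0 + β2 + β3 (kit), β0 + β3 (control with TENS) and β0 (control without). So β2 is kit minus control with TENS: all-era kit against later-era controls again. In a cross-sectional simulation with k = 24, the absolute bias was 0.063 SD for a 0.2 SD shift and 0.127 SD for 0.4 SD, the same in this model as in the per-protocol analysis. Adding a before/after indicator to either model brought it to about zero, with a type I error of about 5%.

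**Which analyses are exposed.** The model printed in 9.4.4 has no baseline or arm-by-time term, so an era difference in PF level enters β2 directly. It also enters the arm effect of the repeated mixed model unless baseline is adjusted for. A constant level difference cancels in the difference-in-differences analysis of 9.4.2; an era difference in change, or in who responds, does not.

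**The case against.** This is a sensitivity analysis beside a retained ITT analysis, and the plan itself warns of bias. No passage counts the early kit patients or dates the TENS change; that date may have stood on pages not available for review. The era shifts are assumed, and the second survey route is offered as an alternative means of collecting the same PROs. Encounter month could adjust for calendar time. All of this limits the size of the claim. It does not remove the defect: the general caveat neither names the source nor corrects it, and encounter month is neither committed to nor in the printed model.

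A reader might infer more than the documents support:

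- **That the headset changes confound the comparison.** Only kit patients use a headset, so this is a change of treatment version.
- **That the daily TENS questionnaire adds to the problem.** It separates the early controls from everyone else, so dropping them improves comparability on that item.
- **That the survey and site changes coincide with the TENS change.** Without its date, which changes fall on which side is unknown, and a set restricted to the later era might still span some of them. Its arms would nevertheless be concurrent.
- **That every planned estimate is biased by a level shift.** The difference-in-differences is not.

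**Conclusion.** The concern holds as a design flaw in the two analyses that 9.4.4 adds: the per-protocol exclusion breaks concurrency in one arm, and the TENS-term model's arm coefficient inherits it. The imbalance is 32% against 0% early patients (24% against 0% on the other reading), assuming about 24 early kit patients. The consequence is conditional: 0.06 to 0.10 SD of bias for assumed era shifts of 0.2 to 0.3 SD, below the 0.2 SD MCID, with false-positive rates of about 6–7% and 8–9%. Actual size and direction are unknown. The finding does not show that the trial's result is biased, and the ITT analysis does not share this one-sided exclusion. It should be corrected before analysis because the correction is simple and these results will be read as support for the main one.

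**What to change.** In 9.4.4, state the date on which TENS was added to the control arm and define the sensitivity set as all participants, in both arms, randomised on or after it. Alternatively, keep all kit patients and prespecify a before/after-change indicator. Add the same indicator to the TENS-term model in either case. Report the numbers randomised per arm before and after the date. Reconcile the 20 subjects mentioned at the end of 9.4.4 with the 24 given elsewhere.

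Cost with k = 24: the comparison becomes 51 v 75, and SE = sqrt(1/51 + 1/75) = 0.181 SD against 0.163, a rise of about 11%. The indicator gives the same arm SE, because the early kit patients then inform only the era term; the choice costs nothing in precision. At 25% loss, power for 0.6 SD (noncentral t) is about 81% (38 v 56) instead of 88% (56 v 56), and 76% if 33 kit patients were early (32 v 56). With the indicator in the TENS-term model, the TENS coefficient becomes imprecise: sqrt(1/24 + 1/24 + 1/51 + 1/75) = 0.34 SD. The arm coefficient, which the plan calls the term of interest, keeps its SE of 0.181 SD.
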